4.3 SUBGROUP AND STRATIFIED ANALYSES

For the primary effectiveness endpoints, all data will be included in the primary analysis. By the nature of the study, the results will be stratified by age group (subjects aged 6-13.9

Statistical Analysis Plan

years and subjects aged 14-70 years). Additional subgroup or stratified analyses may be presented. These may include but are not limited to:

- Day and night (daytime: 6AM to <12AM; nighttime as 12AM to <6AM)
- Length of time in HCL (e.g., Month 1, Month 2)
- Demographic measures (e.g., gender, race, additional age breakdowns)
- Previous pump or CGM use
- BMI (≤ 25 vs > 25 kg/m²)

5 ANALYSIS OF SAFETY

All adverse events reported during the study will be reviewed and adequately reported to comply with applicable regulations. All reportable AEs will be assessed by the investigator who will determine whether the event is related to the study procedures or related to the study device and whether the event meets any of the criteria for seriousness. The event will be considered serious if the event meets at least one criterion for seriousness.

5.1 MEDICAL MONITOR

An independent Medical Monitor will be responsible for individual and timely review of adverse events. The Medical Monitor will also adjudicate all serious adverse events (SAEs), including events of severe hypoglycemia and diabetic ketoacidosis (as well as all events reported by the investigator as being device-related) for seriousness, severity, relationship to study device and procedure, whether the event is anticipated or unanticipated, and event categorization. The adjudication decision by the Medical Monitor will be used for the final classification of adverse events for regulatory reports, product labeling, and publications or presentation.

5.2 RELATIONSHIP TO STUDY DEVICE AND PROCEDURE

The causal relationship to the study procedures and the investigational device for each adverse event will be rated as follows:

- Unrelated: The event is not related to the procedures or the investigational device.
- Possibly Related: The temporal sequence is such that the relationship is not unlikely or there is no contradicting evidence that can reasonably explain the subject's condition. There is a possibility of any relation between the event and the procedures or the investigational device.
- Related: The temporal sequence is relevant or the event abates upon completion of the procedure/ investigational device, or the event cannot be reasonably explained by the subject's condition or comorbidities. The event is related or most likely associated with the procedures or the investigational device.

Statistical Analysis Plan

For the purposes of dichotomizing the causal relationship in safety summaries, events that are “Related” or “Possibly Related” will be considered related.

5.3 SEVERITY

The severity of the adverse event will be rated based upon the following grades:

- Mild: Usually transient, requires no special treatment, and does not interfere with the participant's daily activities
- Moderate: Usually causes a low level of inconvenience, discomfort or concern to the participant and may interfere with daily activities, but is usually ameliorated by simple therapeutic measures and participant is able to continue in study
- Severe: Interrupts a participant's usual daily activities, causes severe discomfort, may cause discontinuation of study device, and generally requires systemic drug therapy or other treatment

5.4 ANALYSIS OF ADVERSE EVENTS

Safety summaries and analyses will be based on all subjects that are enrolled in the study (i.e., Intention to Treat analysis set). All adverse events reported over the course of the study will be summarized and tabulated by study phase, event category, seriousness, severity, and relationship to the study procedures and the investigational device. Except where indicated, a subject reporting the same adverse event more than once will be counted once when calculating the number and percentage of subjects with that particular event.

Adverse events leading to death or to discontinuation from the study will be listed separately. A listing of all adverse events will be provided. The primary safety endpoints will be presented by existing Dexcom G6 use at the time of screening (users and non-users) and by participation in the prepivotal study (those who participated in the prepivotal study and those who did not). No formal tests of hypotheses are proposed for the safety endpoints.

Adverse events that were reported during study pause will be listed separately.

5.5 EVALUATION OF DEVICE DEFICIENCIES

Device deficiencies will be tabulated and listed in a manner similar to the methods described for adverse events. Any device deficiency leading to an adverse event or study termination will be listed separately.

Device deficiencies that were reported during study pause will be listed separately.

Statistical Analysis Plan

6 ANALYSIS OF SECONDARY EFFECTIVENESS ENDPOINTS

The secondary effectiveness objective is to evaluate additional glycemic measures of effectiveness of the Omnipod Horizon™ Automated Glucose Control System. The secondary effectiveness objective will be evaluated based on the following per subject endpoints:

- A1C
 - A1C after at least 8 weeks of continuous Phase 2 participation, at the end of Phase 2 (Visit 13), 6 months (Visit 16) and the end of Phase 3 (Visit 19)
 - Change from baseline in A1C after at least 6 weeks of continuous Phase 2 participation, after at least 8 weeks of continuous Phase 2 participation, at the end of Phase 2 (Visit 13), 6 months (Visit 16) and the end of Phase 3 (Visit 19)
 - Proportion of subjects demonstrating an improvement from baseline in A1C after at least 6 weeks of continuous Phase 2 participation, after at least 8 weeks of continuous Phase 2 participation, at the end of Phase 2 (Visit 13), 6 months (Visit 16) and the end of Phase 3 (Visit 19)
- Glucose metrics from system CGM during the hybrid closed-loop phase for Phase 2 will be compared to Phase 1 during the day, overnight, and overall:
 - Mean glucose
 - Percentage of time in range 70-180 mg/dL
 - Percentage of time in range 70-140 mg/dL
 - Percentage of time in range > 180 mg/dL
 - Percentage of time in range ≥ 250 mg/dL
 - Percentage of time in range ≥ 300 mg/dL
 - Percentage of time in range < 70 mg/dL
 - Percentage of time in range < 54 mg/dL
 - Standard deviation
 - Coefficient of variation
- Percentage of time in hybrid closed-loop as proportion of overall device usage time during Phase 2 and Phase 3
- Glucose management indicator (GMI) based on overall mean glucose during Phase 2 and Phase 3 will be compared to Phase 1
- Insulin requirements during Phase 2 and Phase 3 will be compared to Phase 1:
 - Total daily insulin (TDI) (units, units/kg)
 - Total daily basal insulin (units, units/kg)
 - Total daily bolus insulin (units, units/kg)
- Change from baseline in BMI (kg/m²) at end of Phase 2 and Phase 3

Statistical Analysis Plan

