#### 6.2.1 Primary Effectiveness Endpoints

There are two primary effectiveness endpoints.

- A1C after at least 6 weeks of continuous Phase 2 participation compared to baseline
- A1C at Visit 16, 19, 21, and 23 compared to baseline
- Percentage of time in range (70-180 mg/dL) during Phase 2 and separately during Phase 3 of the hybrid closed-loop phase as compared to Phase 1 (standard therapy)

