#### 6.3.1 Secondary Endpoints

The secondary objective will be evaluated using the following per subject endpoints *with* prespecified hypotheses:

- Glucose metrics from system CGM during the hybrid closed-loop phase for Phase 2 will be compared to Phase 1 overall:
  - % of time > 180 mg/dL
  - % of time < 70 mg/dL

Additional per subject secondary endpoints *without* prespecified hypotheses used to evaluate the secondary objective include:

- A1C:
  - A1C after at least 8 weeks of continuous Phase 2 participation at the end of Phase 2 (Visit 13), at 6 months (Visit 16), and at the end of Phase 3 (Visit 23; approximately 15 months)
  - Change from baseline in A1C after at least 6 weeks of continuous Phase 2 participation, after at least 8 weeks of continuous Phase 2 participation at the end of Phase 2 (Visit 13), at 6 months (Visit 16), and at the end of Phase 3 (Visit 23; approximately 15 months)
  - Proportion of subjects demonstrating an improvement from baseline in A1C after at least 6 weeks of continuous Phase 2 participation, after at least 8 weeks of continuous Phase 2 participation at the end of Phase 2 (Visit 13), at 6 months (Visit 16), and at the end of Phase 3 (Visit 23; approximately 15 months)
- Glucose metrics from system CGM during the hybrid closed-loop phase during Phase 2, and separately during Phase 3, will be compared to Phase 1 during the day, overnight, and overall:
  - Mean glucose
  - % of time in range 70-180 mg/dL
  - % of time in range 70-140 mg/dL
  - % of time > 180 mg/dL
  - % of time  $\geq$  250 mg/dL
  - % of time  $\geq$  300 mg/dL
  - % of time < 70 mg/dL
  - % of time < 54 mg/dL
  - Standard deviation
  - Coefficient of variation
- Percentage of time in hybrid closed-loop as proportion of overall device usage time during Phase 2, and separately during Phase 3
- Glucose management indicator (GMI) based on overall mean glucose during Phase 2, and separately during Phase 3 will be compared to Phase 1
- Insulin requirements during Phase 2, and separately during Phase 3 will be compared to Phase 1:
  - Total daily insulin (TDI) (units, units/kg)
  - Total daily basal insulin (units, units/kg)
  - Total daily bolus insulin (units, units/kg)
- Change from baseline in BMI (kg/m^2) at end of Phase 2, and at end of Phase 3.

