#### 13.2.2.1 Primary Effectiveness Endpoints

There are two primary effectiveness endpoints.

- A1C after at least 6 weeks of continuous Phase 2 participation compared to baseline
- A1C at Visit 16, 19, 21, and 23 compared to baseline
- Percentage of time in range (70-180 mg/dL) during Phase 2 and separately during Phase 3 of the hybrid closed-loop phase as compared to Phase 1 (standard therapy)

#### A1C – Phase 2

A1C after at least 6 weeks of continuous Phase 2 participation will be compared to baseline A1C as measured by the core laboratory by calculating the change from baseline in A1C at the appropriate follow-up visit for each subject. Given the nature of this measure, continuous device use is essential for unbiased measurement of A1C. Therefore, the follow-up A1C used in the analysis of this endpoint will include only data from the subjects with at least 6 weeks of continuous Phase 2 participation, either prior to study pause or after recommencement, depending on the length of continuous participation and availability of the A1C measurements. The A1C collected at the latest follow-up visit during Phase 2 will be used, assuming it was collected after at least 6 weeks of subject's participation in Phase 2.

The change in A1C is calculated as A1C at follow-up minus baseline A1C (where negative change indicates decrease or improvement in A1C). The null hypothesis associated with this endpoint states that the mean change in A1C is greater than or equal to zero. Rejection of the null hypothesis indicates that the observed data support the alternative hypothesis that the mean change in A1C is less than zero.

The hypotheses associated with the first primary endpoint are defined as:

$$H_0: \mu \geq 0$$

$$H_1: \mu < 0$$

where  $\mu$  is the mean of the per subject differences in A1C from baseline to follow-up.

#### A1C – Phase 3

A1C at Visit 16 (~6 months total HCL participation) will be compared to baseline A1C as measured by the core laboratory by calculating the change from baseline in A1C at follow-up visit for each subject.

The change in A1C is calculated as A1C at follow-up minus baseline A1C. There are no hypotheses associated with this endpoint.

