### **Percentage of Time in Range 70-180 mg/dL – Phase 3**

The percentage of time in range 70-180 mg/dL during Phase 3 of the hybrid closed-loop phase will be compared to standard therapy by calculating the change between the time in range percentages between Phase 3 of hybrid closed-loop and Phase 1 (standard therapy) for each subject. The change in percentage of time in range 70-180 mg/dL is calculated as the percentage of time in range during Phase 3 minus the percentage of time in range during Phase 1. There are no hypotheses associated with this endpoint.

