1 PURPOSE

The purpose of this Statistical Analysis Plan (SAP) is to describe the statistical methodology that will be used to confirm the safety and effectiveness of the Omnipod Horizon™ Automated Glucose Control System in patients with type 1 diabetes. Should there be any discrepancy between the pivotal study protocol and this SAP, the content of the SAP shall prevail.

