3.2 PRIMARY EFFECTIVENESS OBJECTIVE AND ENDPOINTS

The primary effectiveness objective is to evaluate the effectiveness of the Omnipod Horizon™ Automated Glucose Control System. The primary effectiveness objective will be evaluated by analyzing the following endpoints:

- A1C after at least 6 weeks of continuous Phase 2 participation compared to baseline
- Percentage of time in range 70-180 mg/dL during Phase 2 of the HCL phase compared to Phase 1 (ST)

Statistical Analysis Plan

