3.3 SECONDARY OBJECTIVE AND ENDPOINTS

The secondary objective is to evaluate additional glycemic measures of effectiveness of the Omnipod Horizon™ Automated Glucose Control System. The secondary objective will be evaluated based on the following per subject endpoints *with* prespecified hypotheses:

- Glucose metrics from system CGM during the hybrid closed-loop phase for Phase 2 will be compared to Phase 1 overall:
 - Percentage of time in range > 180 mg/dL
 - Percentage of time in range < 70 mg/dL

Additional per subject endpoints *without* prespecified hypotheses used to evaluate the secondary objective include:

- A1C:
 - A1C after at least 8 weeks of continuous Phase 2 participation at the end of Phase 2 (Visit 13), 6 months (Visit 16) and the end of Phase 3 (Visit 19)
 - Change from baseline in A1C after at least 6 weeks of continuous Phase 2 participation, after at least 8 weeks of continuous Phase 2 participation, at the end of Phase 2 (Visit 13), 6 months (Visit 16) and the end of Phase 3 (Visit 19)
 - Proportion of subjects demonstrating an improvement from baseline in A1C after at least 6 weeks of continuous Phase 2 participation, after at least 8 weeks of continuous Phase 2 participation, at the end of Phase 2 (Visit 13), 6 months (Visit 16) and the end of Phase 3 (Visit 19)
- Glucose metrics from system CGM during the hybrid closed-loop phase for Phase 2 and Phase 3 will be compared to Phase 1 during the day, overnight, and overall:
 - Mean glucose
 - Percentage of time in range 70-180 mg/dL
 - Percentage of time in range 70-140 mg/dL
 - Percentage of time in range > 180 mg/dL
 - Percentage of time in range ≥ 250 mg/dL
 - Percentage of time in range ≥ 300 mg/dL
 - Percentage of time in range < 70 mg/dL
 - Percentage of time in range < 54 mg/dL
 - Standard deviation
 - Coefficient of variation
- Percentage of time in hybrid closed-loop as proportion of overall device usage time during Phase 2 and Phase 3
- Glucose management indicator (GMI) based on overall mean glucose during Phase 2 and Phase 3 will be compared to Phase 1
- Insulin requirements during Phase 2 and Phase 3 will be compared to Phase 1:

Statistical Analysis Plan

- Total daily insulin (TDI) (units, units/kg)
- Total daily basal insulin (units, units/kg)
- Total daily bolus insulin (units, units/kg)
- Change from baseline in BMI (kg/m^2) at end of Phase 2 and Phase 3

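### The SAP is inconsistent on which Phase 3 effectiveness results are reported and at what rank, and it ends Phase 3 at Visit 19 where the protocol ends it at Visit 23

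*SAP*

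**What the plan says.** **Protocol.** Sections 6.2.1 and 13.2.2.1 list under primary effectiveness endpoints "Percentage of time in range (70-180 mg/dL) during Phase 2 and separately during Phase 3 of the hybrid closed-loop phase", each against Phase 1, and A1C at Visits 16, 19, 21 and 23 against baseline. For Phase 3 time in range, 13.2.2.1 adds: "There are no hypotheses associated with this endpoint". Section 13.5 extends this to all Phase 3 endpoints. Section 6.3.1 also lists the CGM metrics, including time in range 70-180 mg/dL, as secondary endpoints "during Phase 2, and separately during Phase 3, will be compared to Phase 1 during the day, overnight, and overall". Phase 3 lasts 12 months and ends at Visit 23, Day 450 (Protocol Summary, Table 3, 10.9).

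**SAP.** Sections 3.2 and 4 name two primary effectiveness endpoints, A1C and time in range, both for Phase 2 only. Section 3.3 lists ten CGM metrics as secondary, "for Phase 2 and Phase 3 will be compared to Phase 1 during the day, overnight, and overall". Section 6 repeats the ten metrics, but "for Phase 2 will be compared to Phase 1 during the day, overnight, and overall". Section 6.1 carries the primary time-in-range method over to the other ranges. Phase 3 lasts 6 months (2.3) and ends at Visit 19 (3.3, 6, 6.6, 7.6).

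**Precedence.** SAP 1: "Should there be any discrepancy between the pivotal study protocol and this SAP, the content of the SAP shall prevail". Protocol 13.11 says the same.

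**The concern.** Two sections of one SAP give the same endpoint list with different phases, so a programmer working from SAP 6 and one working from SAP 3.3 would produce different table sets. The protocol's Phase 3 primary comparisons are also missing from the SAP's primary list, and the precedence rule favours the SAP.

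What is at stake is the rank of these endpoints and certainty about what will be reported. Phase 3 supplies the longer-term glycemic results, and the protocol says they will be submitted separately. If the sponsor has to choose between SAP sections once Phase 3 data are in hand, the choice is open to a charge of selective reporting, even if it is made in good faith.

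**Working it through.** **1. The plan's own figures.** The point disputes no number, but the sample sizes show what Phase 3 does and does not touch. For a paired t-test, power = 1 − F(t(1−α, n−1); n−1, (δ/σ)√n), where F is the noncentral t distribution function and α is one-sided 0.0125.
- A1C: δ = 0.5, σ = 0.8. The smallest n for 90% power is 35 (power 90.6%), as stated.
- Time in range: δ = 10, σ = 15. The smallest n is 31 (power 90.5%), as stated.
- Alpha: 0.0125 + 0.0125 = 0.025.

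All inputs are Phase 2 quantities. No Phase 3 endpoint has a hypothesis, alpha or power.

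**2. Endpoint lists side by side.**

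| Item | Protocol | SAP 3.2 and 4 (primary) | SAP 3.3 (secondary) | SAP 6 (secondary analysis) |
|---|---|---|---|---|
| Time in range 70-180, Phase 3 | Primary (6.2.1, 13.2.2.1); also secondary (6.3.1) | Absent | Present | Absent |
| Other nine CGM metrics, Phase 3 | Secondary | n/a | Present | Absent |
| GMI, closed-loop time, insulin, BMI, Phase 3 | Secondary | n/a | Present | Present |
| A1C, Visits 16 and 19 | Primary | Absent | Present | Present |
| A1C, Visits 21 and 23 | Primary | Absent | Absent | Absent |

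The CGM bullet is the only one in SAP 6 that loses Phase 3 relative to SAP 3.3. That looks like an omission, because GMI in the same list requires Phase 3 mean glucose.

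**3. Does another SAP section close the gap?** SAP 6.1 refers to the primary time-in-range method, which 4.2 defines as Phase 2 minus Phase 1. It allows the range to change but says nothing about the phase. SAP 7.1 says all available data will be used to summarize Phase 3 endpoints, but does not say which those endpoints are.

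**4. Size of the internal conflict.** 10 metrics × 3 windows = 30 Phase 3 comparisons that are in SAP 3.3 and not in SAP 6. SAP 6.3 gives GMI = 3.31 + 0.02392 × mean glucose, so overall Phase 3 mean glucose is in effect still compared. That leaves 30 − 1 = 29 with no equivalent in SAP 6.

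**5. Length of Phase 3.** Nominal visit days from protocol Tables 2 and 3: Visit 13 = Day 94, Visit 19 = Day 270, Visit 23 = Day 450.
- Protocol's Phase 3: 450 − 94 = 356 days, or 356/450 = 79% of device days.
- SAP's Phase 3: 270 − 94 = 176 days, or 176/270 = 65%.
- Beyond the SAP's end of Phase 3: 450 − 270 = 180 days, with A1C due at Visits 21 and 23.

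The mismatch also affects BMI. SAP 6.6 takes end-of-Phase-3 values from Visit 19, but protocol 10.5 schedules no height or weight there; in Phase 3 they are scheduled at Visit 23 (10.9) and at early withdrawal (10.11).

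**The case against.** **SAP 6 does analyse Phase 3.** A reader might infer from the CGM bullet that no Phase 3 glucose comparison is planned there. The text does not support that: SAP 6 keeps Phase 3 GMI, A1C, closed-loop time, insulin and BMI. What is missing is the ten-metric list.

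**Omission is not exclusion.** SAP 6 does not forbid Phase 3 CGM summaries, and nothing says that it overrides SAP 3.3. Section 3.3 agrees with protocol 6.3.1 and, read with 7.1, can be taken to retain the summaries. The precedence rule is no obstacle here, because it covers protocol-SAP differences and this conflict is inside the SAP. All of this stands. It shows that a sensible reading exists, but the text does not require it.

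**The protocol is itself untidy on rank.** It announces two primary effectiveness endpoints, then lists three bullets that include Phase 3 items, and it also lists Phase 3 time in range as secondary. So SAP 3.3 is not wrong to call it secondary. The loss of rank comes from its absence in SAP 3.2 and 4.

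**The SAP may have been written for the Phase 2 submission, or may lag the protocol.** SAP 2.3 mentions that submission, and the 6-month Phase 3 fits a lag. But the SAP includes Phase 3 endpoints throughout, and neither document mentions a separate Phase 3 SAP. A lag would explain the missing Visits 21 and 23. It would not explain why SAP 3.3 and 6 disagree.

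**The consequence is limited.** Phase 3 endpoints have no hypotheses, study success rests on Phase 2 safety rates (SAP 2.5), and SAP 4.2 says the primary effectiveness endpoints will not support labeling claims. This stands and sets the weight of the point.

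**Conclusion.** The inconsistency is real and should be corrected, as a matter of endpoint rank and descriptive reporting. Thirty Phase 3 comparisons depend on which SAP section is followed. Phase 3 time in range and four A1C visits lose their primary listing, and two of those visits (21 and 23) have no analysis anywhere in the SAP.

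Three stronger conclusions are tempting but unsupported. The documents do not show a threat to type I error, power or the Phase 2 success criterion. They do not show that Phase 3 glucose goes unanalysed. The 79% share of device days is not the size of the problem either: it holds only on the protocol's Day 450 and is 65% on the SAP's Day 270, and the data are collected on either reading.

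The verdict assumes that no separate Phase 3 analysis plan exists outside these documents, and it uses nominal visit days without windows.

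**What to change.** 1. Align SAP 2.3, 3.3, 6, 6.6 and 7.6 with the protocol's 12-month Phase 3 ending at Visit 23. Without this, the steps below would add visits that fall after the SAP's own end of Phase 3.
2. In SAP 6, extend the CGM bullet to Phase 2 and, separately, Phase 3, each against Phase 1. In SAP 6.1, let the phase be updated as well as the range.
3. In SAP 3.2 and 4, add Phase 3 time in range 70-180 mg/dL and A1C at Visits 16, 19, 21 and 23 as descriptive primary effectiveness endpoints without hypotheses. Where the SAP counts two primary effectiveness endpoints, say two Phase 2 primary effectiveness endpoints with hypotheses, so that the one-sided 1.25% tests stay with those two.

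The cost is SAP wording and repeated table shells. No new data are needed and no alpha is spent.
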